7.7.2. Rescue Criteria

A rescue algorithm is provided to minimize participants having an inadequate response to the treatment for their anemia for an extended period of time and to enable consistency in the application of rescue therapy across the study. Details are provided in [Table 7](#).

This rescue algorithm **does not** apply to participants with low Hgb as a result of an acute or subacute event with an identifiable cause (e.g., GI bleed, blood loss due to surgery or vascular access). In these cases, treatment should be directed to the specific cause and randomized treatment will be continued at the current dose (unless Hgb is ≥ 13 g/dL which requires a dose hold).

Table 7 Rescue Algorithm for Anemia Management

Evaluate Participant for Rescue starting from Week 4 if:	

 • HemoCue Hgb is <7.5g/dL, or • HemoCue Hgb is <8.5g/dL and participant is symptomatic¹, or • HemoCue Hgb is <8.5 g/dL on three consecutive visits 	
Step 1: Initial Intervention	
Initial intervention depends on the participant's iron status:
 
 • If participant has TSAT < 15% and/or Ferritin < 50 ng/mL from a prior study visit, then 
 ○ continue with study treatment, and ○ intervene with iron therapy: Single dose of IV iron up to 1000 mg (in addition to the iron management criteria) 
At the next study visit in 4 ±1 weeks, recheck HemoCue Hgb. If HemoCue Hgb value continues to meet the evaluation criteria for rescue, then Proceed to Step 2.
 
 • If participant has TSAT ≥15% and Ferritin ≥ 50ng/mL, proceed to step 2.
Step 2: Rescue	
Randomized treatment should be permanently discontinued (but participant should remain in study to monitor Hgb) and the participant should be rescued according to local clinical practice:
 
 • If HemoCue Hgb remains <8.5 g/dL despite Initial Intervention (Step 1) based on the average of two HemoCue Hgb values ² • Rescue can be considered IV iron, rhEPOs and/or Transfusions.

1. Symptoms should be related to anemia of CKD. Further information regarding collecting this data will be stated in the SRM.

2. Repeat HemoCue Hgb at the same study visit to confirm Hgb (using the same sample); take average of 2 values.

The study site will supply any rescue medication that will be obtained locally.

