5.4. Examination of Covariates, Other Strata and Subgroups

- The following is a non-exhaustive list of covariates that may be used in summaries of demographics, descriptive summaries and statistical analyses.
- Additional covariates of clinical interest may also be considered.
- If the percentage of participants is small within a particular subgroup, then the subgroup categories may be refined prior to unblinding the trial.
 - If the category cannot be refined further, then descriptive rather than statistical comparisons may be performed for the particular subgroup
- The primary and principal secondary endpoints will be evaluated for a set of prespecified subgroups. Subgroup analyses are aimed to assess for consistency with the overall result, and they may have low power if the subgroup is small. Statistical models (ANCOVA or CMH chi-squared test) will be adjusted for the covariates used in the original analysis, subgroup, treatment and treatment by subgroup interaction. Point estimates and two-sided 95% CIs will be estimated (presented on Forest Plots) and the subgroup by treatment interaction p-value calculated. Subgroup analyses will not be adjusted for multiplicity.

| Subgroups (Based on status before randomization) | Categories |
|--|--|
| Age | <65 years, ≥65 years - <75 years, ≥75 years |
| Gender | Female, Male |
| Race Group | Summary tables: American Indian or Alaskan Native, Asian, Black, Native Hawaiian or Other Pacific Islander, White, Mixed Race Analysis: American Indian or Alaskan Native, Asian, Black, White (exclude Native Hawaiian or Other Pacific Islander and Mixed Race) |
| Ethnicity | Hispanic, non-Hispanic |
| Region | Per Section 5.3 |
| Baseline BMI | <30kg/m ² , ≥30kg/m ² |

CONFIDENTIAL

205270

| Subgroups (Based on status before randomization) | Categories |
|--|---|
| Baseline Weight | <75kg, ≥75kg |
| Baseline Hgb | <8.5g/dL, 8.5-<9g/dL, 9-10g/dL, > 10g/dL <9g/dL, 9-<10g/dL, 10-11g/dL, >11g/dL |
| Serum Iron Levels at Baseline | TSATs≥15% and Ferritin≥50 ng/mL vs TSATs<15% or Ferritin<50 ng/mL |
| Iron Replete Participants | TSATs≥20% and Ferritin≥100 ng/mL vs TSATs<20% or Ferritin<100 ng/mL |
| hsCRP | Quartile Analysis |
| Diabetic | Yes, or No |
| History of Heart Failure | Yes, or No |
| eGFR | <15, ≥15 |
| ADPKD (Autosomal Dominant Polycystic Kidney Disease) | ADPKD, non-ADPKD Note: Only used for analyses of eGFR |

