7.2.4. Strategy for Intercurrent (Post-Randomization) Events

For the first principal secondary endpoint of % of participants having a Hgb increase of ≥ 1.0 g/dL from baseline to EP, a treatment policy strategy will be used in the analysis to include all on and off treatment Hgb values of the ITT populations, including values taken after rescue and IP discontinuation.

The following are the intercurrent events for the first principle secondary efficacy analysis:

- Death prior to the end of the EP (i.e. before Week 28 visit)
- Randomized treatment discontinuation prior to the end of the EP
- Use of non-randomized ESA medications for any reason including rescue prior to the end of the EP
- Receipt of blood transfusions prior to the end of the EP

Except for the intercurrent event of deaths prior to the end of the EP, a treatment policy strategy will be used in which all scheduled Hgb data recorded during the EP (Weeks 24-28) will be included in the primary efficacy analysis, regardless of discontinuation of study medication due to any reasons, and regardless of receipt of non-randomized ESA medications for any reason including rescue, or blood transfusions. For deaths, a hypothetical strategy will be used as described in Section [7.2.5.2](#)

The following are causes of missing Hgb data affecting the first principle secondary efficacy endpoint that are not due to intercurrent events:

- Study withdrawal prior to the end of the EP
- Permanent switching from clinic visits to remote visits prior to start to EP
- Intermittent missing Hgb values at one or more visits with the EP

Missing data will be imputed as described in Section [7.2.5.2](#).

For the second principal secondary endpoint of mean change in SF-36 vitality sub-score between baseline and Week 28, a hypothetical strategy will be used assuming subjects had not had intercurrent events specified below. Data collected after IP discontinuation will not be included in the statistical analysis and will be treated as missing data. The missing SF-36 vitality sub-scores will be imputed as outlined in Section [7.2.5.2](#).

The following are the intercurrent events for the second principle secondary efficacy analysis:

- Death prior to the end of the EP (i.e. before Week 28 visit)
- Randomized treatment discontinuation prior to the end of the EP

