7.2.5.2. Statistical Methodology Specification

| Endpoint / Variables |
|--|
| 
 • % of participants having a Hgb increase of ≥ 1.0 g/dL from baseline to EP. • Mean Change in SF-36 Vitality domain between baseline and Week 28 |
| Model Specification |
| 
 • For the first principal secondary endpoint of % of participants having a Hgb increase of ≥ 1.0 g/dL from baseline to EP, the EP Hgb value will be defined as the mean of all available Hgb values (on and off-treatment) during the EP (Week 24 to Week 28 inclusive). A Cochran-Mantel-Haenszel (CMH) chi-squared test, adjusting for treatment, and region (see Section 5.3), will be used to make comparisons between the treatment groups. A treatment policy strategy will be used in the analysis to include all on and off treatment Hgb values of the ITT populations, including values taken after rescue and IP discontinuation. • For the second principal secondary endpoint of mean change in SF-36 vitality sub-score |

CONFIDENTIAL

205270

between baseline and Week 28, a hypothetical strategy will be used which includes only on-treatment values and exclude the measures taken after IP disc/rescue medication. The SF-36 vitality sub-scores will be imputed if missing. An ANCOVA model will be used including factors for baseline score, treatment, and region.

Model Results Presentation

- For the first principal secondary endpoint, the number and % of participants having a Hgb (on and off-treatment) increase of ≥ 1.0 g/dL from baseline to EP by treatment group, relative response rate (daprodustat vs. placebo) and two-sided 95% CI will be provided along with the one-sided CMH p-value for the treatment group comparison.
- For the second principal secondary endpoint, each individual item within the SF-36 vitality subscore will be summarized using mean, standard deviation, minimum, P25, median, P75 and maximum at baseline, Week 8, Week 12, and Week 28 visit by treatment group. (See Section 7.3.2.1)
- For the second principal secondary endpoint, all available SF-36 vitality sub-score change from baseline values (on-treatment only) will also be summarized using mean, standard deviation, minimum, P25, median, P75, and maximum at Week 8, Week 12, and Week 28 visit. (See Section 7.3.2.1)

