- For the second principal secondary endpoint, the LS means estimated from treatment difference, will be presented along with one-sided p-value and 95% CI. The number of participants contributing to the analysis and the associated mean and standard deviation of the baseline and Week 28 SF-36 Vitality sub-score value will also be displayed with the results of the model.
- For the second principal secondary endpoint, all available SF-36 vitality sub-score values (on-treatment) will be displayed graphically for each scheduled study Week 8, Week 12, and Week 28 visit using a line plot.
- For the second principal secondary endpoint, all available SF-36 vitality sub-score change from baseline values (on-treatment) will be displayed graphically for each scheduled study Week 8, Week 12, and Week 28 visit using a line plot. The line plot of mean values \pm standard errors by time will include horizontal reference line to identify zero change, and the number of participants by treatment group contributing to each mean value.
- SF-36 data will be summarized and analysed using both norm-based and traditional scoring, see Section 10.6.5 for details. The traditional scoring will be considered as the primary results and norm-based as supportive results.

Multiple Imputation HGB Increase ≥ 1.0 g/dL

- For the first secondary endpoint, the imputed data from the primary endpoint will be used for deriving the % of participants having a HGB increase of ≥ 1.0 g/dL from baseline to EP.

Multiple Imputation SF-36 Analysis

- For the SF-36 principle secondary endpoint, multiple imputation analysis will be performed using on treatment SF-36 values and conducted under a set of assumptions about missing sf-36 values (see Section 10.6.3).
 - Missing scheduled SF-36 data in both arms through Week 28 will be considered MAR and imputed using PROC MI procedure with NIMPUTE = 200 and FCS to generate 200 datasets. The seed for reproducibility is set to 205270. The imputations will be done by randomized treatment, include region as categorical covariate.
 - Week 28 SF-36 values will be computed and compared across treatment groups using the principle secondary ANCOVA model described above. Rubin's rules [Rubin, 1987]

CONFIDENTIAL

205270

- will be used to combine results of the imputed datasets using SAS PROC MIANALYZE procedure. As a result, a single estimated treatment difference and its standard error will be produced, with which a 95% CI will be calculated.

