- Subjects with scheduled off-treatment SF-36 data will be imputed assuming they were on treatment.
 - The low and high cutoffs at SF-36 values of 0 and 100 for traditional scoring and 22.89 and 70.42 for norm-based scoring will be applied to all imputed SF-36 values.
 - For the SF-36 principle secondary endpoint supportive analysis imputing subjects who have remote/over the phone SF-36 visits during Week 28 and those subjects who were treatment interrupted prior to their Week 28 visit will be performed using on treatment SF-36 values and conducted under a set of assumptions about missing sf-36 values (see Section 10.6.3). This is a similar imputation strategy as outlined above but will be based on on-treatment SF-36 values and consider those subjects who completed SF-36 remotely/over the phone or who were treatment interrupted prior to Week 28 as missing.

Supportive Analyses

- For the first principal secondary endpoint, a supportive analysis using while alive and on treatment strategy (on-drug analysis) will be performed using a Cochran-Mantel-Haenszel (CMH) chi-squared test, adjusting for treatment, and region (see Section 5.3), will be used to make comparisons between the treatment groups. No imputation will be performed for this analysis.
- For the second principal secondary endpoint, a treatment policy strategy (on and off treatment) analysis will be performed using an ANCOVA model including all participants with on and off treatment values, including factors for baseline score, treatment, and region. This will be done for both traditional and norm-based scoring. No imputation will be performed for this analysis.
- For the second principal secondary endpoint, a while alive and on treatment strategy (on treatment only) analysis will be performed using an ANCOVA model including all participants with on treatment values, excluding subjects who IP discontinue/rescue, including factors for baseline score, treatment, and region. This will be done for both traditional and norm-based scoring. No imputation will be performed for this analysis.

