- For the second principal secondary endpoint, an analysis imputing subjects who have remote/over the phone SF-36 visits during Week 28 and those subjects who were treatment interrupted prior to their Week 28 visit will be performed using an ANCOVA model including factors for baseline score, treatment, and region. This analysis will be based on the hypothetical strategy outlined above. This will be done for both traditional and norm-based scoring. This analysis will only be performed if at least 10% of the ITT population is identified to have remote/over the phone SF-36 visits during Week 28 and those subjects who were treatment interrupted prior to their Week 28 visit have observed week 28 SF-36 data.

Subgroup Analyses

- For the first principal secondary endpoint, subgroup analysis will be performed using all available Hgb values (on and off-treatment). A Cochran-Mantel-Haenszel (CMH) chi-squared test, adjusting for treatment and subgroup, will be used to make comparisons between the treatment groups. A treatment policy strategy will be used in the analysis to include all on and off treatment Hgb values of the ITT populations, including values taken after rescue and IP discontinuation. The imputed data from the primary endpoint will be used for deriving the % of

CONFIDENTIAL

205270

participants having a HGB increase of ≥ 1.0 g/dL from baseline to EP.

- For the second principal secondary endpoint, subgroup analyses will be performed using an ANCOVA model, including factors for baseline score, treatment, region, subgroup and subgroup treatment interaction. A hypothetical strategy will be used as defined above. The SF-36 vitality sub-scores after IP discontinuation will be imputed based on the conservative assumption that there is no change in the sub-scores after the intercurrent event, so the last available on-treatment values (or baseline values if there is no on-treatment values) will be used in the imputation. This will be done for both traditional and norm-based scoring.

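### The SF-36 Vitality subgroup analysis carries scores forward after treatment discontinuation, while the overall result it is meant to check uses MAR multiple imputation as if on treatment

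*SAP*

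**What the plan says.** **Overall analysis.** SAP 7.2.4 states that for SF-36 Vitality "a hypothetical strategy will be used assuming subjects had not had intercurrent events specified below". The events are death and discontinuation of randomized treatment before the end of the evaluation period. SAP 7.2.5.2 describes the same strategy as one in which "a hypothetical strategy will be used which includes only on-treatment values and exclude the measures taken after IP disc/rescue medication". Its multiple imputation block adds that "Missing scheduled SF-36 data in both arms through Week 28 will be considered MAR" and are imputed by FCS into 200 datasets, by randomized treatment with region as a covariate, and pooled by Rubin's rules. It also says "Subjects with scheduled off-treatment SF-36 data will be imputed assuming they were on treatment".

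**Subgroup analysis.** The Vitality bullet under Subgroup Analyses in 7.2.5.2 refers back to that hypothetical strategy. It then assumes, and calls conservative, that scores stay unchanged once the event has occurred: "so the last available on-treatment values (or baseline values if there is no on-treatment values) will be used in the imputation". Both traditional and norm-based scoring are covered.

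**Purpose.** SAP 5.4: "Subgroup analyses are aimed to assess for consistency with the overall result".

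**Neighbouring rules.** The Hgb responder subgroup analysis in 7.2.5.2 reuses the imputed data from the primary endpoint. SAP 10.6.3 applies Rubin's rules to the primary Hgb subgroup analyses. In the list of displays, the note to Table 2.18 (overall Vitality) names the hypothetical imputation strategy. The notes to Tables 2.32 and 2.33 (Vitality by subgroup) say only that imputation is included.

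**The concern.** Imputing as if treatment had continued and imputing no change since the last on-treatment visit are different assumptions about the same missing scores. A subgroup row and the overall row on one forest plot would then differ partly because of method. Two subgroups with the same true effect but different discontinuation would tend to appear to differ.

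There is a plausible route to such differences. Persistently low Hgb leads through the rescue steps in Protocol 7.7.2 to the instruction "Randomized treatment should be permanently discontinued (but participant should remain in study to monitor Hgb"), and baseline Hgb is one of the subgroup factors. Discontinuation could therefore vary by arm and by that factor.

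The list of displays contains no carry-forward estimate for the whole population, so a reader could not separate method from subgroup. Carry-forward is also single imputation, so the subgroup intervals do not reflect imputation uncertainty as the overall interval does.

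**Working it through.** **1. The plan's own figure.** Protocol 10.2.1 gives a 5-point effect, SD 21, 540 evaluable participants and 79% power. SE = 21 × √(2/270) = 1.807; 5/1.807 − 1.96 = 0.81; Φ(0.81) = 0.79. It reproduces, and the mismatch does not touch it.

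**2. The two rules side by side, for scores after discontinuation.**

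| | Overall | Subgroups |
|---|---|---|
| Assumption | as if still on treatment | no change since last on-treatment visit |
| Imputed value | MAR draw by arm | last on-treatment score, or baseline |
| Imputations | 200, Rubin's rules | one |

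**3. Is carry-forward conservative?** Take on-treatment mean changes of 8 (daprodustat) and 3 (placebo), a true difference of 5.0. Let 10% and 30% discontinue, with baseline carried forward. Expected difference = 8 × 0.9 − 3 × 0.7 = 7.2 − 2.1 = 5.1, which is above 5.0. With 10% in both arms it is 7.2 − 2.7 = 4.5. The direction depends on the discontinuation pattern.

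**4. Assumptions for the size of the interaction shift.** From the Protocol: effect 5 at Week 28, SD 21, 300 per arm. Assumed: two equal subgroups (150 per arm in each), visit correlation 0.5, and all discontinuation rates. Protocol 10.2.1 gives only up to 10% study withdrawal before Week 24. The ANCOVA residual SD is 21 × √(1 − 0.5²) = 18.19, so the interaction SE with complete data is 18.19 × √(4/150) = 2.97.

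**5. Equal discontinuation by arm, 10% in one subgroup and 30% in the other.** Take a gradual effect (2.5, 3.75 and 5 at Weeks 8, 12 and 28) and random discontinuation spread evenly over the three intervals.
- Mean effect carried forward: (0 + 2.5 + 3.75)/3 = 2.08.
- Shortfall per discontinuing pair: 5 − 2.08 = 2.92.
- Spurious interaction: (0.30 − 0.10) × 2.92 = 0.58.

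Simulations under several dropout models give about 0.5 to 0.7. At most this is 0.7/2.97 = 0.24 SE.

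**6. Placebo participants in one subgroup at 30%, everyone else at 10%.** With a flat placebo course and random dropout, the carried-forward mean equals the Week 28 mean, so the shift is 0. If low scorers leave, their low scores are frozen instead of regressing toward the mean. Placebo then looks worse and the effect in that subgroup looks larger. If scores also rise 6 points in both arms, random dropout alone gives about 0.20 × (6 − 2.5) = 0.7. Here 2.5 is the mean rise carried forward when the rise is 3, 4.5 and 6 at the three visits. Simulated shifts, by log-odds slope of discontinuation per SD of the last score:

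| Course | Slope 0 | 0.5 | 1.0 |
|---|---|---|---|
| Flat | about 0 | 0.9 | 1.5 |
| Rising 6 in both arms | 0.8 | 1.6 | 2.4 |

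The largest is 2.4/2.97 = 0.81 SE. At slope 1.0 the realised discontinuation rates run several points above the nominal ones.

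**7. Overall effect by carry-forward, 12% daprodustat and 25% placebo, flat course.** The shifts are −0.35, +0.23 and +0.70 at slopes 0, 0.5 and 1.0, giving 4.65, 5.23 and 5.70 against a true 5. The sign changes with the dropout mechanism alone.

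**The case against.** The best defence is that the carry-forward sentence is a deliberate, specific override. The Model Specification in 7.2.5.2 states the strategy (on-treatment values only) separately from the imputation, so the sentence can be executed, with scores missing while on treatment still going to MAR imputation. A reason is given too: the assumption is called conservative. That much stands, so a claim that the SAP offers no justification would be wrong. What is missing is a reason for departing from the overall method.

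Subgroup results are also unadjusted, acknowledged to be possibly low-powered, and given no interaction threshold in SAP 5.4. With equal discontinuation by arm the distortion would hardly be visible. The larger figures depend on an assumed dropout slope and correlation, and at slope zero with a flat course the shift vanishes. This too stands, and is why a range is shown.

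Three stronger readings are tempting and unsupported:
- **That the confirmatory Vitality test is compromised.** It uses the MAR imputation, and subgroup analyses lie outside the hierarchy in SAP 5.5.
- **That carry-forward will overstate the effect.** Under random dropout it can understate it (step 7).
- **That baseline Hgb subgroups will discontinue differently.** This is an inference. Protocol 5.4 expects few drop-outs for lack of effect, and no discontinuation rate is given.

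**Conclusion.** The inconsistency is in the text and nothing elsewhere in the documents resolves it. The subgroup analysis claims the overall strategy, but imputes post-discontinuation scores under a different assumption, with no matching overall estimate listed for comparison (the mock shells are not in the available text). The description of carry-forward as conservative is not assured.

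The consequence is confined to exploratory subgroup estimates, interaction p-values and forest plots. It is small if the arms discontinue alike. It could approach one interaction standard error if discontinuation is concentrated among low-scoring placebo participants in one subgroup while scores rise in both arms. All of these sizes rest on assumed rates, correlation, time course and dropout mechanism. This should be corrected before unblinding, but it does not threaten the trial's main conclusions.

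**What to change.** Replace the carry-forward sentence with the MAR multiple imputation used for the overall analysis. Fit the specified subgroup ANCOVA in each imputed dataset, and pool the subgroup estimates and the interaction by Rubin's rules, for both scorings.

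Preferably add the subgroup variable to the imputation model where category sizes allow, because leaving it out pulls a real interaction toward zero. In an illustrative simulation with a true 8-point interaction and 10% discontinuation in both arms, the shift was −0.60 without the variable and +0.01 with it. For sparse categories SAP 5.4 already provides a route: "If the percentage of participants is small within a particular subgroup, then the subgroup categories may be refined prior to unblinding the trial", or descriptive presentation. Otherwise reuse the main imputed datasets, as the SAP does for the Hgb subgroups, and state that limitation.

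If carry-forward is kept, label it a sensitivity analysis, show the overall estimate by the same method, and delete both the reference back to the earlier definition and the word conservative. In either case name the imputation method in the notes to Tables 2.32 and 2.33.

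**Cost.** SAP wording and, for the preferred version, one imputation run per factor and scoring (about 13 factors besides region). Interaction standard errors were about 5%, 12% and 21% wider than under carry-forward at 10%, 20% and 30% discontinuation in the illustrative simulations. No data collection changes.
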